## SMW Study Manual of Procedures

---

```
        else P&TT._short_sitbout_ct=0;
IF status in (&P.) and act_intensity=0 and interval_s>=1800 then P&TT._long_sitbout_dur=gap;
        else P&TT._long_sitbout_dur=0;
IF status in (&P.) and act_intensity=0 and interval_s<1800 then P&TT._short_sitbout_dur=gap;
        else P&TT._short_sitbout_dur=0;
IF status in (&P.) and act_intensity=1 then P&TT._Stand=gap;
        else P&TT._Stand=0;
IF status in (&P.) and act_intensity=2 then P&TT._LPA=gap;
        else P&TT._LPA=0;
IF status in (&P.) and act_intensity=3 then P&TT._MVPA=gap;
        else P&TT._MVPA=0;
IF status in (&P.) and activitycode=2 then P&tt._step_min=gap;
        else P&tt._step_min=0;
IF status in (&P.) and activitycode=2 then P&tt._step_ct=1;
        else P&tt._step_ct=0;
IF status in (&P.) and activitycode=2 then DO;
        if stepboutdur<5 then P&tt._step00_05=gap;
            else P&tt._step00_05=0;
        if 5<=stepboutdur<10 then P&tt._step05_10=gap;
            else P&tt._step05_10=0;
        if 10<=stepboutdur<15 then P&tt._step10_15=gap;
            else P&tt._step10_15=0;
        if 15<=stepboutdur<30 then P&tt._step15_30=gap;
            else P&tt._step15_30=0;
        if 30<=stepboutdur<60 then P&tt._step30_60=gap;
            else P&tt._step30_60=0;
        if 60<=stepboutdur<90 then P&tt._step60_90=gap;
            else P&tt._step60_90=0;
        if 90<=stepboutdur<120 then P&tt._step90_120=gap;
            else P&tt._step90_120=0;
        if stepboutdur>=120 then P&tt._step120_up=gap;
            else P&tt._step120_up=0;
        End;
```

%MEND; \*Ends macro;

%PERIOD(1); \*Runs for P1 variables;

%PERIOD(2); \*Runs for P2 variables;

%PERIOD(3);

%PERIOD(4);

%PERIOD(5);

## SMW Study Manual of Procedures

---

Run;

```
data Lis;  
set APwake;
```

```
IF Workday=2 or WorkDay=0 THEN Status=1; /*nonworkday*/  
    IF Workday=1 AND WorkTM <= datetime3 <= OffWorkTM THEN Status=2; /*atwork*/  
    IF Workday=1 AND not (WorkTM <= datetime3 <= OffWorkTM) THEN  
Status=3; /*offwork*/
```

Run;

```
%Macro Pattern(tt);  
%If &tt.=1 %then %do;  
%Let P=1;  
%end;  
%If &tt.=2 %then %do;  
%Let P=2;  
%end;  
%If &tt.=3 %then %do;  
%Let P=3;  
%end;  
%If &tt.=4 %then %do;  
%Let P=2 3;  
%end;  
%If &tt.=5 %then %do;  
%Let P=1 2 3;  
%end;
```

```
Data Upright; Set Lis;  
where status in (&P.);  
dur_bout = gap/60;
```

\*set activity code to missing for any data that is not valid -

-sleep: exclude

-off time: exclude

-not valid day (for the type of day in question): exclude

-not part of the time you are interested in as appropriate - eg not work hours;

```
Activity_code2 = Activitycode;
```

```
if delete=1|validday_est=0 then do;
```

```
Activity_code2 = . ;
```

```
dur_bout = . ;
```

## SMW Study Manual of Procedures

---

```
end;
```

```
*split the actual valid time into bouts of upright/ not;  
ActUpright =0;  
if Activity_code2 in (1,2) then ActUpright = 1;  
if ActUpright = 1 then newupbout = 1;  
if ActUpright = 1 & ActUpright = lag(ActUpright) then newupbout = 0;
```

```
newbout = 0;  
if Activity_code2 in (.,0) then newbout = 1;  
if Activity_code2 in(1,2) & newupbout=1 then newbout = 1;  
run;
```

```
data upright2;  
set upright;  
by ID;  
if first.ID then newboutid = 0;  
if newbout = 1 then newboutid + 1;  
run;
```

```
proc means data = upright2 noprint;  
by ID newboutid;  
where ActUpright = 1;  
output out=upright3  
sum (dur_bout) = dur_actbout  
;  
run;
```

```
data upright3;  
set upright3;  
ln_dur_actbout = log(dur_actbout);  
drop _type__freq_;  
run;
```

```
proc means data = upright3 noprint;  
by ID;  
output out=upright4  
  
                    mean(ln_dur_actbout) = mn_dur_actbout  
                    stddev(ln_dur_actbout) = sd_dur_actbout  
;  
run;
```

\*MEANPERIOD - mean of a lognormal distribution based on mle for a lognormal distribution;

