## SMW Study Manual of Procedures

---

```
*import AP event file;
DATA import;
    INFILE "&&filepath&i"
           LRECL=32760
    ENCODING="WLATIN1"
    TERMSTR=crlf
    DLM=','
    MISSOVER
           firstobs=2
    DSD ;
    INPUT Datetimevar
           Count
           Intervalold_s
           ActivityCode
           APCumulativeStepCount
           APActivityScoreMEThr
           validday_est
           Sleepbout
           ID
           Mtime
           ;
    boutid = _N_;
    sasdatetimenumber = (Datetimevar - 21916)*86400;*convert exceldate to
sasdatetime;
    CumulativeStepCount_i = APCumulativeStepCount;
    steps_n = APCumulativeStepCount - lag(CumulativeStepCount_i);
    if boutid = 1 then
        steps_n = APCumulativeStepCount;

    if Datetimevar in (0,.) then
        delete;          *remove rows of 0s from end of some activpal event files;
    if intervalold_s in (0,.) then delete;
    drop CumulativeStepCount_i;*non cumulative steps;
    if intervalold_s>=21600 then delete=1;else delete=0;

RUN;

*recalculate intervals as time between each bout -> more precise than the rounded data;
proc Sort data =import;
    by id descending boutid;
run;

data events (drop= Datetimevar intervalold_s APcumulativestepcount);
```

```
set import;
boutidR = _N_;
sasdatetimenumber_endbout = lag(sasdatetimenumber);

if sasdatetimenumber_endbout = . & sasdatetimenumber ne . then
    sasdatetimenumber_endbout = sasdatetimenumber + Intervalold_s;
Interval_s = sasdatetimenumber_endbout -
    sasdatetimenumber;
basicdate = datepart(sasdatetimenumber);
noondate = datepart(sasdatetimenumber + 43200);

*dates at beginning of bout
for day and for noon to noon window;
format sasdatetimenumber sasdatetimenumber_endbout datetime26.6 basicdate
noondate ddmmyy10.;
run;

proc Sort data =events;
    by id boutid;
run;

*Expand each event into 1-seconds epochs;

DATA events2; SET events;
If interval_s>=1 then interval_p=floor(interval_s);
    else if interval_s<1 then interval_p=interval_s;

do _i_ = 0 to Interval_s-(Interval_s/interval_p) by (Interval_s/interval_p); *preserves elapsed
time of non-whole number intervals;
    datetime3=sasdatetimenumber+_i_;
    output;
end;
format datetime3 datetime26.6 date date9.;
Run;

*recalualte interval between each epoch;

Proc sort data=events2;
by descending datetime3;
run;

data events2;set events2;
gap=lag(datetime3)-datetime3;
if gap>=1 then p=floor(gap);
```

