## SMW Study Manual of Procedures

---

```
        else if gap<1 then p=gap;
date=datepart(datetime3);
if gap=. then delete;
```

```
run;
```

```
Proc sort data=events2;
by datetime3;
run;
```

```
*pull log data;
```

```
DATA windows3(drop=gap date noondate mtime); SET track.masterlogs2;
    WHERE ID=&&i&i*1;
    IF bedtime=. then delete;
```

```
        IF new_ootm=. then delete;
RUN;
```

```
*Merge logs with activpal data;
```

```
PROC SQL;
    CREATE TABLE APwake AS
    SELECT      t1.id,
                t1.Mtime,
                t1.Datetime3,
                t1.sasdatetimenumber,
                t1.sasdatetimenumber_endbout,
                t1.validday_est,
                t1.basicdate,
                t1.noondate,
                t1.activitycode,
                t1.Count,
                t1.gap,
                t1.Interval_s,
                t1.Steps_n,
                t1.boutid,
                t1.delete,
                t2.new_ootm,
                t2.bedtime,
                t2.MTS,
                t2.Sleeptime,
                t2.wake_freq,
                t2.total_time_awake,
```

```
t2.waketime,  
t2.ootm,  
t2.Workday,  
t2.MOT_to,  
t2.WorkTM,  
t2.OffWorkTM,  
t2.MOT_off,  
t2.Start,  
t2.End,  
t2.impute
```

```
FROM events2 AS t1  
NATURAL JOIN windows3 AS t2  
WHERE t1.datetime3 BETWEEN t2.new_ootm AND t2.Bedtime  
ORDER BY t1.ID, t1.datetime3;
```

```
QUIT;
```

```
RUN;
```

\* export dataset to create intermediate files that can be re-analyzed for later use;

```
Data "X:\[name] Lab\Stand and Move  
ASU_UMN\Data\ActivPAL\ISO_TEST\SAS_FILES\DATASETS\MetaData\APWake_&&i.._T  
&&Mtime&i"; set ApWake;  
Run;
```

\*Calculate cadence;

```
data step; set APwake;
```

```
Activity_code2 = Activitycode;
```

\*calculating a 0/1 variable for whether the event is stepping (and relevant, to be included) or not;  
ActStep =0;

```
if Activity_code2 =2 then ActStep = 1;
```

```
if ActStep = 1 then newstepbout = 1;
```

\*calculating a 0/1 variable for whether the relevant stepping event is part of a new stepping bout  
or not;

```
if ActStep = 1 & ActStep = lag(ActStep) then newstepbout = 0;
```

```
newbout = 0;
```

```
if Activity_code2 in (.,0,1) then newbout = 1;
```

```
if Activity_code2 =2 & newstepbout=1 then newbout = 1;
```

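### Upright bouts are numbered after each period is cut out, so upright bouts on successive workdays can be joined, which on average slightly inflates the at-work mean upright bout length

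*Combined protocol and SAP*

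**What the plan says.** All references are to the SAS code in Appendix 1.4.

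- **Row order.** When logs are merged with monitor data, epochs of about one second are sorted by participant and time across all days: "ORDER BY t1.ID, t1.datetime3".
- **At-work rows.** These lie between self-reported arrival and departure on a workday: "IF Workday=1 AND WorkTM <= datetime3 <= OffWorkTM THEN Status=2". The prefix P2 marks this period; P3 marks the remaining waking time on workdays.
- **Period cut.** In the Pattern macro, the step that builds the Upright dataset keeps only rows of the requested period, by a clause beginning "where status in (&P".
- **Stated intent.** A comment in the same step lists time whose activity code is to be set to missing. The list includes time that is "not part of the time you are interested in as appropriate - eg not work hours".
- **What is set to missing.** Only rows meeting "if delete=1|validday_est=0 then do", that is, events of six hours or more and invalid days.
- **Bout rule.** An upright row continues the current bout when the previous retained row is upright: "if ActUpright = 1 & ActUpright = lag(ActUpright) then newupbout = 0". A sitting or missing row starts a new number. The counter resets only at a new participant.
- **Output.** Durations are summed within bout number and logged. `mean_period` is exp(mean + variance/2) of the logs, one value per participant and period. The report template carries it for all five periods.

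**The concern.** Once off-work rows are gone, the row before this morning's logged arrival is the last row before the previous workday's logged departure. Someone on their feet at both moments has two separate bouts treated as one. For P3, upright time before arrival can be joined in the same way to upright time after departure on the same day.

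This looks like a coding slip, because the comment describes a treatment (missing, not removed) that would end the bout. The sedentary block does not have the problem, since it groups rows by the device's own bout identifier. At stake is a descriptor of how long people stay upright at work before sitting again, and its error would depend on the number of workdays recorded and on bouts per day.

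**Working it through.** **Does the join happen?** Take two workdays with upright bouts of 5, 2 and 4 minutes each, upright at the first departure and the second arrival.

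- As written: 5, 2, 4 + 5 = 9, 2, 4. That is five bouts totalling 22 minutes, with arithmetic mean 22/5 = 4.40. The logs have mean 1.316 and variance 0.411, so `mean_period` = exp(1.316 + 0.411/2) = 4.58 minutes.
- With out-of-period rows kept as missing: six bouts, arithmetic mean 22/6 = 3.67. The logs have mean 1.230 and variance 0.183, so `mean_period` = exp(1.230 + 0.183/2) = 3.75 minutes.
- If either boundary epoch is sitting, both versions give six bouts and 3.75 minutes.

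The result is the same whether LAG runs on every row or only when the first condition is true. Epoch durations are set before the cut ("gap=lag(datetime3)-datetime3"), so the join adds no overnight hours to the upright bout.

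**Ceiling for an arithmetic mean.** Section 10.3 specifies seven days of wear. Assuming five workdays, there are at most four joins. With k bouts a day, the largest inflation is 5k/(5k − 4) − 1:

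- k = 10: 50/46 − 1 = 8.7%
- k = 20: 100/96 − 1 = 4.2%
- k = 30: 150/146 − 1 = 2.7%
- k = 50: 250/246 − 1 = 1.6%

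**The statistic the code reports.** This was simulated with lognormal bouts, log-SD 1.3 and five workdays. The median does not matter, because the relative change is scale-free. Edge bouts were either full length or cut to a uniform 2% to 100% of their length, to mimic logged clock times falling mid-bout. All of these inputs are assumptions. The table gives average inflation:

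| Bouts/day | Day pairs joined | Edge bouts full | Edge bouts cut |
|---|---|---|---|
| 10 | all | 10.5% | 4.2% |
| 15 | half | 3.3% | 1.3% |
| 15 | all | 6.8% | 2.4% |
| 20 | half | 2.4% | 0.9% |
| 20 | all | 5.1% | 1.6% |
| 30 | half | 1.6% | 0.5% |

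With two workdays, 15 to 20 bouts a day and full-length edges, inflation is about 1.5% to 2.2% if half the pairs join and 3.1% to 4.2% if all do. With one workday it is zero.

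A wider grid of 48 scenarios (10 to 50 bouts a day, log-SD 1.2 or 1.5, edges unchanged, cut or lengthened) gave average changes from +0.1% to +11.4%.

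**Sign for an individual.** With cut edges, only about 61% to 71% of simulated participants in that grid had a higher value. Joining two short fragments lowers the log variance, which can outweigh the longer bout. Example: 5, 2, 0.1 | 0.1, 2, 5 minutes. Kept separate, the logs have mean 0 and variance 3.349, giving exp(1.674) = 5.34. Joined (5, 2, 0.2, 2, 5), they have mean 0.599 and variance 1.734, giving exp(0.599 + 0.867) = 4.33.

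**Stepping block.** The cadence block uses the same rule ("if ActStep = 1 & ActStep = lag(ActStep) then newstepbout = 0") but numbers bouts before any period cut, so it avoids the at-work join. It has no night break either. Stepping at logged bedtime and at the next logged rise would form one bout whose clock duration, `be_dt - bs_dt`, includes the night.

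**The case against.** The strongest objection is materiality. The primary outcomes are at-work sitting and LPA, the secondary outcome is cardiometabolic risk, and section 12.1 otherwise names sit-stand transitions among the monitor outcomes. `mean_period` appears in no aim or analysis paragraph, nor in the list of outputs at the head of the code. The sitting, LPA and transition variables are summed by date from a different dataset, which the Pattern macro does not touch. All of this stands.

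A second objection is that the join is conditional. The boundaries are self-reported clock times, so posture at that second is unknown, and the documents give no frequency. This also stands. Walking in and out makes upright boundaries plausible but does not establish them.

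A reader might infer three stronger things that the documents do not support:

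- **Every pair of workdays is joined.** A sitting or missing row retained at either boundary prevents it.
- **Every participant's value is too high.** That holds for an arithmetic mean whenever a join occurs, but the lognormal mean can fall.
- **The arms are affected differently.** STAND+ aims for standing during half of desk-based time, so bout patterns could differ, but nothing in the documents or the simulations shows a difference, its direction or its size.

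**Conclusion.** The defect is real and can be read directly from the code. Numbering follows the cut, nothing tests date or contiguity, and the code departs from its own comment. Its effect on `P2_mean_period` is an average upward shift of modest size: about 1.6% to 10.5% with full-length edge bouts and about 0.5% to 4% when logged times cut them. Both ranges rest on five workdays, 10 to 30 bouts a day, log-SD 1.3, and half to all day pairs upright at both ends. None of the bout counts, the spread or the join share comes from the documents, and a lower join share would give less. This is a minor correction to a derived output. It does not bear on the primary or secondary conclusions.

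**What to change.** Number upright bouts on all waking rows before the period restriction, then keep the rows of the period. Alternatively, drop the restriction in that step and set `Activity_code2` and `dur_bout` to missing for out-of-period rows, as the comment intends.

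In either case, force a new bout when a row is not contiguous with the one before it or the log day changes. For example, after the existing lag line add `if datetime3 - lag(datetime3) > 5 then newupbout = 1;`. Events of a second or more are split into epochs of at least one and under two seconds, so five seconds is a safe threshold. The break is needed with either option, because no waking rows separate one logged bedtime from the next rise.

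Add the same break to the stepping block for `newstepbout`. This may slightly change the off-work split between LPA and MVPA, because cadence uses `be_dt - bs_dt`. Report that change if it occurs.

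The cost is a few lines of SAS and a rerun, with no new data. Counting the joins during the rerun would replace the assumed share with an observed one.

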## SMW Study Manual of Procedures

---

```
data upright4 (keep =ID P&tt._mean_period);
set upright4;
P&tt._mean_period = exp(mn_dur_actbout + ((sd_dur_actbout**2)/2));
run;
```

```
*Recombine sedentary bouts;
Data sedbt;set lis;
    if delete=1|validday_est=0 then delete;
```

```
Run;
```

```
proc means data=sedbt nonobs noprint;
by id boutid;
output out= sedbt2
    sum(gap) = gap
    mean(status) = status
    mean(activitycode) = activitycode;
```

```
Run;
```

```
*** sedentary accumulation;
data sed (keep = ID boutid dur_sed);
Set sedbt2;
where status in (&P.);
if Activitycode = 0;
```

```
dur_sed = gap/60;
run;
```

```
proc sort data = sed;
by ID dur_sed;
run;
```

```
proc means data=sed noprint;
by ID;
output out=summary min(dur_sed)=P&tt._min_t_sit max(dur_sed)=P&tt._max_t_sit
sum(dur_sed)=P&tt._totsed ;
run;
```

```
data sed;
merge sed summary;
by ID;
```

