## SMW Study Manual of Procedures

---

```
If delete=1 then delete;* remove potential non-wear: bouts>6 hrs;
run;
```

```
data step2;
set step;
by id;
*numbering the stepping bouts [newboutid];
if first.id then newboutid = 0;
if newbout = 1 then newboutid + 1;
run;
```

```
proc means data = step2 noprint;
by id newboutid;
where ActStep = 1;
output out=step3 min(sasdatetimenumber)=bs_dt max(sasdatetimenumber_endbout)=be_dt
sum(steps_n)=steps_n;
;
run;
```

```
data step3 (keep= ID newboutid cadence stepboutdur);
set step3;
*date the stepping bout began for later aggregation;
```

```
basicdate = datepart (bs_dt);
*duration of the stepping bout;
stepboutdur = be_dt - bs_dt;
```

```
*cadence;
cadence = 2*steps_n/(stepboutdur/60);
```

```
run;
```

```
Proc SQL;
    Create table cadence as
        select a.*,
               b.Cadence,
               b.stepboutdur
    From step2 as a
    Left join step3 as b
    on a.ID=b.ID and a.newboutid=b.newboutid
    order by a.Datetime3;
Quit;
```

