## SMW Study Manual of Procedures

---

\*categorize epochs into either SED STAND LPA MVPA;

Data cadence2(drop=sasdatetimenumber);set cadence;  
if start<=datetime3<=end then delete; \*Delete errors/non-wear time;

date=datepart(datetime3);

IF Workday=2 or WorkDay=0 THEN Status=1; /\*nonworkday\*/  
IF Workday=1 AND WorkTM <= datetime3 <= OffWorkTM THEN Status=2; /\*atwork\*/  
IF Workday=1 AND not (WorkTM <= datetime3 <= OffWorkTM) THEN  
Status=3; /\*offwork\*/  
  
IF activitycode=2 AND cadence ge 100 THEN act\_intensity=3; /\*MVPA\*/  
ELSE IF activitycode=2 AND cadence lt 100 then act\_intensity=2; /\*LPA\*/  
ELSE IF activitycode=1 THEN act\_intensity=1; /\*Standing\*/  
ELSE IF activitycode=0 THEN act\_intensity=0; /\*Sitting\*/

%MACRO PERIOD(tt); \*Defines macro with variable (I chose to call it tt for time) that will be set  
to 1-5;

%If &tt.=1 %then %do;

%Let P=1;

%end;

%If &tt.=2 %then %do;

%Let P=2;

%end;

%If &tt.=3 %then %do;

%Let P=3;

%end;

%If &tt.=4 %then %do;

%Let P=2 3;

%end;

%If &tt.=5 %then %do;

%Let P=1 2 3;

%end;

IF status in (&P.) then P&TT.=gap; else P&TT.=0;

IF status in (&P.) and act\_intensity=0 then P&TT.\_Sit=gap;  
else P&TT.\_Sit=0;

IF status in (&P.) and act\_intensity ge 1 and lag(act\_intensity)=0 then P&TT.\_Sitstand=1;  
else P&TT.\_SitStand=0;

IF status in (&P.) and act\_intensity=0 and interval\_s>=1800 then  
P&TT.\_long\_sitbout\_ct=1/floor(interval\_s);  
else P&TT.\_long\_sitbout\_ct=0;

IF status in (&P.) and act\_intensity=0 and interval\_s<1800 then  
P&TT.\_short\_sitbout\_ct=1/floor(interval\_s);

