## SMW Study Manual of Procedures

---

```

sum(P5_Stand)/60 as P5_Stand,
sum(P5_LPA)/60 as P5_LPA,
sum(P5_MVPA)/60 as P5_MVPA,
sum(P5_step_min)/60 as P5_step_min,
sum(P5_step_ct) as
P5_step_ct,
sum(P5_step00_05)/60 as
P5_step00_05,
sum(P5_step05_10)/60 as
P5_step05_10,
sum(P5_step10_15)/60 as
P5_step10_15,
sum(P5_step15_30)/60 as
P5_step15_30,
sum(P5_step30_60)/60 as
P5_step30_60,
sum(P5_step60_90)/60 as
P5_step60_90,
sum(P5_step90_120)/60 as
P5_step90_120,
sum(P5_step120_up)/60 as
P5_step120_up
```

```
FROM cadence2
GROUP BY ID, Mtime, Date;
QUIT;
```

```
Data sittostand2; Merge sittostand Ap_var;
by ID;
Run;
```

```
PROC APPEND DATA=sittostand2 out=iso.REPORT_FINAL FORCE;
RUN;
%end;
/*proc Datasets lib=work nolist kill;*/
/* quit;*/
/**/
/* run;*/
%MEND APimport;
```

\*nominate folder to find the events files, followed by \, such as;

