## SMW Study Manual of Procedures

---

```
%let dir = X:\[name] Lab\Stand and Move
ASU_UMN\Data\ActivPAL\ISO_TEST\SAS_FILES>taggedfiles\T1;
%APimport;

proc printto;
run;

%put END TIME: %sysfunc(datetime(),datetime14.);
%put PROCESSING TIME:
%sysfunc(putn(%sysvalf(%sysfunc(TIME())-&datetime_start.),mmss.)) (mm:ss) ;

Proc SQL;
Create table Activpal as
select a.*,
       b.workday
From iso.Report_Final as a
Left join track.masterlogs2 as b
ON a.ID=b.ID and a.date=b.date
Order by a.ID, a.date;
Quit;

Data iso.AP_Final;
set Activpal;

if workday=0 and p1_min<600 then valid_p1=0;
if workday=0 and p1_min>=600 then valid_p1=1;
if workday=1 and p2_min<240 then valid_p2=0;
if workday=1 and p2_min>=240 then valid_p2=1;
if workday=1 and p3_min<240 then valid_p3=0;
if workday=1 and p3_min>=240 then valid_p3=1;

run;
```

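### In the Appendix 1.4 code the sedentary-pattern variables rest on a different time base from the sitting totals, and sitting bouts that cross arrival or departure are lost even from the combined periods

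*Combined protocol and SAP*

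**What the plan says.** The SAS code in Appendix 1.4 gives each one-second epoch a status: 1 on a non-workday, 2 at work, 3 off work on a workday. It reports five periods: P1 (status 1), P2 (2), P3 (3), P4 (2 and 3) and P5 (1, 2 and 3).

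**Totals route.** Events of 6 h or more are flagged, "if intervalold_s>=21600 then delete=1;else delete=0", and removed, "If delete=1 then delete;* remove potential non-wear: bouts>6 hrs". The step that creates `cadence2` then removes the Start/End windows, "if start<=datetime3<=end then delete", which its comment describes as errors and non-wear. Sitting, standing, LPA and sit-stand transitions are counted epoch by epoch and summed per day "FROM cadence2".

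**Pattern route.** The data set `Lis` starts again from `APwake`, the table that precedes the Start/End deletion. For sedentary bouts it removes flagged events and one kind of invalid day, "if delete=1|validday_est=0 then delete". It then collapses each bout with "mean(status) = status" and selects bouts by "where status in (&P", that is, by an exact match to the period's codes. The results are computed per participant over all days and merged onto every day row.

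**Day rule.** Section 10.3 excludes days with less than 10 h of wear or less than 4 h of work-time wear. The 4 h work rule appears in the code only in the last data step (`AP_Final`), for example "if workday=1 and p2_min<240 then valid_p2=0".

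**The concern.** Total sedentary time from the pattern block stands beside the sitting total in the same file, with the same period label, so a user would expect the two to cover the same time. They do not, for three reasons:

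- an averaged status code cannot match an integer list when a bout crosses the workplace boundary;
- one cleaning step is present in one route and absent from the other;
- the pattern values are pooled over days before the work-wear rule is evaluated.

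At stake are alpha, x50, Gini, shortest and longest bout, bout counts and total sedentary time. The second and third reasons also touch the mean upright period. Any later analysis of how sitting is accumulated would carry these differences without a warning.

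**Working it through.** There is no stated figure to reproduce. The check is a trace of the two routes, with small constructed days run through both. Clock times and bouts are invented for illustration; status codes, period lists and deletion rules are those in the code.

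**1. Bouts that cross arrival or departure.** Let f be the share of a bout's epochs at work. Then mean status = 2f + 3(1 − f) = 3 − f. For 0 < f < 1 this lies strictly between 2 and 3, so it matches none of (2), (3), (2 3) or (1 2 3).

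Constructed day: work 08:00–17:00; sitting 07:30–08:30, 09:00–12:00, 13:00–16:00 and 16:20–18:00.

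- First bout: (30×3 + 30×2)/60 = 2.5. Last bout: (40×2 + 60×3)/100 = 2.6. Both are dropped everywhere.
- P2: totals 30 + 180 + 180 + 40 = 430 min; pattern block 180 + 180 = 360 min.
- P3: totals 30 + 60 = 90 min; pattern block 0.
- P4 and P5: totals 430 + 90 = 520 min; pattern block 360 min. The shortfall of 160 min is the two whole bouts (60 + 100), all of which belong in these periods.

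How often such bouts occur is not in the documents. For illustration only, assume an 8.5 h workday, 60–75% of it sitting, mean sitting bout 5–20 min, lognormal lengths with CV 1.5, and logged times unrelated to posture. The simulated loss from P2 is then 9.9 to 46.6 min per workday, or 3.2% to 12.2% of at-work sitting. If people are usually on their feet at the logged times, the loss is smaller.

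**2. Start/End windows.** In the totals route the 6 h flag acts before the Start/End deletion. What the latter removes is therefore time that the flag did not catch, and the pattern block keeps that time on days it does not drop.

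- Two 2 h sitting events at work, one marked by Start/End: totals 120 min, pattern block 240 min.
- A marked single event of 6.5 h plus 30 min of other sitting: 30 min in both routes, because the 6 h flag removes the event from each.

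So only shorter windows, or windows made of several events, remain.

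**3. Day validity.** `validday_est` is read from the event file before the work log is joined, and is nowhere defined. Take one valid day with 240 min of at-work sitting and a second day with 3 h of work wear (below the 240 min threshold) and 120 min of sitting.

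- If the flag is 1 on the second day, the pattern block pools 240 + 120 = 360 min, and dropping that day's row later cannot undo it.
- If the flag is 0, the pattern block holds 240 min, while the totals hold 360 min until the day is flagged. The totals route never uses `validday_est`.

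**4. Outcomes reached.** Section 12.1 names LPA, sitting, the metabolic risk score and sit-stand transitions. The activPAL outcomes among these come from `cadence2`.

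**The case against.** Several defences are sound and limit the point.

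- **Invalid days.** A reader might infer that days failing section 10.3 are pooled into the pattern values. The documents do not show this. The block drops days with `validday_est` equal to 0, and a comment states the intent to leave out days not valid for the type of day concerned. What stands is that the flag is undefined, so its agreement with the 10 h and 4 h rule cannot be verified.
- **Non-wear.** A reader might infer that the 6 h non-wear rule of section 10.3 is broken. It is not: single events of 6 h or more are removed in both routes. The download instructions define hand-logged non-wear as 6 h of consecutive sitting or standing, which the flag catches when it is one event. That Start/End hold this hand log is itself an inference from a code comment.
- **Long bouts.** It is tempting to say that the lost bouts are mainly the long ones. With CV 1.5, a bout hit by a random clock time has expected length 1 + 1.5² = 3.25 times the mean. That assumes the time is independent of posture. Arrival and departure are self-reported and may well coincide with walking, so this is a model result, not a finding.
- **P2 and P3.** Keeping only bouts wholly inside a period is a defensible choice for a bout-length distribution. That defence does not extend to P4 and P5.
- **Mean upright period.** It selects by epoch status, so the averaging error does not reach it.
- **Relevance.** No aim, no part of section 12.1 and no line of the code's own header list names the pattern variables. This bears on priority, not on whether the values are right.

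**Conclusion.** The point holds in a limited form. Two coding faults can be read directly from the appendix: crossing bouts vanish from P4 and P5, and the pattern block lacks the Start/End deletion. A third matter is unresolved rather than wrong: whether `validday_est` implements the rule in section 10.3.

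P4 and P5 total sedentary time is too low by the full length of every crossing bout. How much that amounts to in this trial cannot be derived from the documents; the range under working rests entirely on assumed bout lengths and on posture being unrelated to the logged times. The effect of the Start/End omission depends on how many shorter or multi-event windows were marked, which is also not given.

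Primary sitting and LPA totals and sit-stand transitions are unaffected. Priority is low, but the code should be corrected before any pattern variable is analysed or shared.

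**What to change.** 1. Add to `Lis` the same Start/End deletion that is applied in `cadence2`.
2. For P4 and P5, select epochs whose status is in the period list first, then sum each `boutid`, instead of filtering on the mean status.
3. For P2 and P3, state one rule for crossing bouts: keep only bouts wholly inside the period, or truncate at the boundary. If truncation is done with a BY summary on id, boutid and status, sort first, because at arrival the status runs 3 then 2 within a bout.
4. If bouts are truncated, use a fixed minimum bout for alpha. The code takes the observed minimum, and truncation creates short fragments: a minimum falling from 10 s to 1 s adds ln(10) = 2.30 to every bout's log term. The code already carries a commented-out alternative with a 10 s minimum.
5. Compute `p2_min` and day validity before the Pattern macro and restrict `Lis` to valid days. Alternatively, define `validday_est` and confirm that it implements the 10 h and 4 h rule.

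The cost is a modest reordering of the macro, since `p2_min` is now computed after the pattern step, plus a rerun. No new data are needed.
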